8.4.5 Baseline Measures of Generalizability of PROUD Trial Clinics

Two randomized and 4 non-randomized clinics from the 5 PROUD trial sites able to provide non-randomized usual care clinics will be compared in the period before randomization to evaluate the degree to which the clinics in PROUD are representative of other PC clinics in each health system. Pre-randomization measures will be identical to primary and secondary outcomes above except that they are measured during the 3 years prior to randomization (Table 9). Other pre-randomization measures include: demographic characteristics (age, sex, race/ethnicity); insurance status (uninsured, state subsidized insurance, private insurance, private pay and Medicare); and the prevalence of OUDs, other substance use and mental health disorders, and chronic pain syndromes; medical comorbidity (Charlson and Elixhauser indices), and the prevalence of prescription opioids (low, medium and high dose) in the PC samples.¹³⁵⁻¹³⁷

Table 9. Example of Secondary Pre-randomization Measures for Comparison of 2 Randomized Clinics to 4 Non-randomized UPC Clinics in the Same Health Care Systems

Recognition of OUD Before Randomization	Number of patients with an ICD code for OUD per 10,000 patients seen during the 3 years prior to randomization
Initiation of OUD treatment before Randomization	Number of patients who meet criteria for OUD treatment above in the 2 years prior to randomization, with no OUD treatment in the preceding year (per 10,000 patients seen)
Retention in OUD treatment before Randomization	Number of patients initiating OUD treatment in the 2 years prior to randomization who receive OUD treatment on 80% of days between initiation and randomization or 365 days whichever comes first

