11.3 Other Secondary Analyses

11.3.1 Representativeness of Randomized UPC Clinics for Usual PC in the 6 Sites

As above, the process of recruitment of sites for the PROUD trial suggested that we did not recruit typical PC clinics. We therefore plan to conduct analyses to compare the recruited (randomized) clinics from each site, to randomly selected PC clinics from the same health system, in the five health systems able to provide data from 4 other PC clinics. These patient level analyses compare patients seen in the randomized PC clinics (2 per site; total clinics =10) to those seen in the other PC clinics that were not included in the trial (4 per site, total clinics=20) in the 3 years prior to randomization. Characteristics to be compared will include the demographics and clinical characteristics of patients visiting the clinics (e.g., mental health diagnoses, substance use disorders diagnoses, medical diagnoses such as HCV⁷³ and HIV, and pain diagnoses, as well as our measure of increased risk for OUDs).

Additionally, we will evaluate whether, for each of the baseline measures of OUD care described above, there is a difference in the measure among randomized clinics compared to 4 non-randomized UPC clinics from the same site, adjusted for differences in patient demographics across the clinics. Specifically, we will fit a mixed effect Poisson regression model of the clinic-level outcome data (e.g., number of patients with an OUD diagnosis during the year prior to randomization). As in our primary outcome model, we will adjust for correlation of outcomes from the same site by including a site-specific random intercept. Specifically, we will consider models of the form

$$\log(E(y_j)) = \log(n) + \alpha + \beta * \text{randomized} + \gamma z + \theta_j,$$

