where y_j denotes the clinic-level outcome (e.g., number of patients with an ICD for OUD during the year prior to randomization), $\log(n)$ denotes an offset for the number of patients who visited the clinic in the year prior to randomization (for the recognition and initiation measures; for the retention measure it corresponds to the number of patients who initiated OUD treatment), *randomized* is an indicator for whether the clinic was included in the trial, z is a vector of demographic covariates being adjusted for (e.g., proportion male, comorbidity rates), and θ_j is a random intercept for site j . The coefficient β corresponds to the adjusted relative rate of the outcome (e.g., recognition of OUD) comparing *randomized* versus non-*randomized* clinics across all sites.

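### Representativeness analysis: the 2-year initiation count is paired with a one-year patient offset, and Table 9 and Section 11.3.1 disagree on the window for recognition

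*Protocol*

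**What the plan says.** Section 8.4.5 of the Protocol sets out the pre-randomization measures for comparing trial clinics with non-randomized usual-care clinics. It describes them as the trial outcomes "except that they are measured during the 3 years prior to randomization (Table 9"). Table 9 then gives the individual measures:

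- Recognition: "Number of patients with an ICD code for OUD per 10,000 patients seen during the 3 years prior to randomization".
- Initiation: "Number of patients who meet criteria for OUD treatment above in the 2 years prior to randomization, with no OUD treatment in the preceding year", scaled per 10,000 patients seen, with no window stated for those patients.
- Retention: built on patients who initiated in the 2 years before randomization.

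Section 11.3.1 fits a clinic-level Poisson model "for each of the baseline measures of OUD care described above". It has a random intercept for site, demographic covariates, and an indicator for being a trial clinic whose coefficient is β. The log(n) term "denotes an offset for the number of patients who visited the clinic in the year prior to randomization (for the recognition and initiation measures"); for retention it is instead the number of initiators. The example outcome in the same sentence is the "number of patients with an ICD for OUD during the year prior to randomization".

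SAP Section 1.1 places the observational analyses in separate analysis plans, which were not available for this review.

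**The concern.** A count and its offset should refer to the same people. If the count runs over two or three years and the offset over one, patients seen only in the earlier years can enter the numerator but not the denominator. The resulting rate is the true rate multiplied by (unique patients over the longer window)/(unique patients in one year). That factor measures patient turnover and says nothing about OUD care. No turnover term appears among the covariates named in 11.3.1.

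The Protocol says openly that the recruited clinics were not typical (Sections 6.4, 10.2.1 and 11.3.1) and relies on these comparisons to judge generalizability. Section 9.5 lists the baseline comparison first among the planned manuscripts. If trial clinics and other clinics in the same system differ in turnover, part of that difference would be reported as a difference in starting OUD treatment and, depending on which section is followed, in recognising OUD.

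**Working it through.** **Windows side by side.**

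| Measure | Count, Table 9 | Count, 11.3.1 | Offset, 11.3.1 | Result |
|---|---|---|---|---|
| Recognition | 3 years, per patients seen in those 3 years | 1 year (given as an example) | patients in 1 year | sections conflict; 11.3.1 read alone is matched |
| Initiation | 2 years | not restated | patients in 1 year | mismatched as written |
| Retention | initiators over 2 years | not restated | number of initiators | not affected |

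**No figure to reproduce.** The documents state no result for this analysis. As a check on the inputs, the twelve 2016 clinic sizes in Table 2 sum to 173,166, or 14,430 per clinic, which agrees with the average of over 14,000 in Protocol Section 2.3.

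**Multi-year against one-year patients.** From Table 2, dividing patients seen in 3 years by the two 2016 clinic sizes combined:

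- HF: 86,262/50,654 = 1.70
- HH: 60,463/29,042 = 2.08
- KPWA: 46,214/29,938 = 1.54
- MF: 34,763/24,073 = 1.44
- MC: 27,031/18,914 = 1.43

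UM is left out because it supplies no non-randomized clinics. These ratios differ by site, but the site intercept largely absorbs between-site differences. Only within-site differences between trial and other clinics can move β appreciably.

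**Illustration of a within-site difference.** Assumptions: clinics in steady state; OUD counts proportional to unique patients in the window; r is the share of 2016 patients also seen in 2014–2015 (Table 2); unique patients over k years = annual n × [1 + (k − 1)(1 − r)]. The two values of r are those of the two trial clinics at each site.

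| System | r (%) | 2-year count / 1-year offset | 3-year count / 1-year offset |
|---|---|---|---|
| HF | 64.0, 67.8 | 1.360/1.322 = 1.03 | 1.720/1.644 = 1.05 |
| HH | 60.7, 64.7 | 1.393/1.353 = 1.03 | 1.786/1.706 = 1.05 |
| KPWA | 76.3, 77.1 | 1.237/1.229 = 1.01 | 1.474/1.458 = 1.01 |
| MF | 73.9, 81.4 | 1.261/1.186 = 1.06 | 1.522/1.372 = 1.11 |
| MC | 75.0, 88.2 | 1.250/1.118 = 1.12 | 1.500/1.236 = 1.21 |

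**Effect on exp(β).** A Poisson model with a log(n) offset was fitted to expected counts for 5 sites, each with 2 trial and 4 other clinics. Fixed site intercepts stood in for the random ones, and the true ratio was 1. One value of r was given to all trial clinics and another to all other clinics.

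- Mismatched windows, equal turnover (r = 75% in both): 1.00 for 2y/1y and 3y/1y.
- Mismatched windows, trial 75.0% and other 88.2%: 1.12 (2y/1y), 1.21 (3y/1y).
- The same gap reversed: 0.89 (2y/1y), 0.82 (3y/1y).
- Count and offset over the same window: 1.00, whatever the turnover.

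**How well the steady-state formula fits.** For three years it predicts 1.64–1.72 at HF (observed 1.70), 1.46–1.47 at KPWA (1.54), 1.37–1.52 at MF (1.44) and 1.24–1.50 at MC (1.43), but 1.71–1.79 at HH (2.08). It is adequate for an order of magnitude and no more.

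**The case against.** The strongest reply is that 11.3.1 defines its recognition outcome over one year, next to a one-year offset. A reader might infer that the model divides a 3-year recognition count by one year's patients, and so that recognition rates are overstated by 43–108% (the ratios 1.43 to 2.08). The documents do not support that. The one-year outcome is only an example, so it does not settle the window, but what is shown for recognition is a contradiction with Table 9. Moreover, exp(β) is a relative rate, and Table 9's own recognition rate already uses a 3-year denominator.

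A reader might also take the 12% and 21% at MC as the bias in β. They are not. They contrast two trial clinics, which carry the same value of the trial indicator, whereas β compares 10 trial clinics with 20 others across five sites. Turnover in those 20 clinics is not reported, so the documents do not show that the ratio is distorted; with equal turnover it is not.

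Three further replies carry less weight. Table 9 is titled as an example, and 11.3.1 speaks only of considering models of this form. Even so, 11.3.1 carries the measures described above it into the model, and no other initiation window is offered. The separate analysis plans may resolve the point, but the Protocol text stays inconsistent until they are seen to do so. Finally, a full 3-year window is not available everywhere: SAP Section 2.3 gives 2.8 years at one system. That affects how the remedy is worded and does not remove the need for it.

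**Conclusion.** The point holds as a specification error for initiation and as a conflict between two sections for recognition. For initiation, a 2-year count is set against one year's patients, and nothing in the documents supplies a matching one-year count. For recognition, Table 9 and 11.3.1 name different windows, and an analyst who took the count from one and the offset from the other would create a 3-year to one-year mismatch.

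Bias in exp(β) is possible but not demonstrated. It requires turnover to differ within systems between trial and non-trial clinics, and the documents do not give the figures that would fix its size or direction. If the gaps resembled those between paired trial clinics in Table 2, a true ratio of 1 would move by about 1–12% for initiation, in either direction. The corresponding 1–21% for recognition applies only under the mixed reading. Both ranges rest on the steady-state assumption, on OUD counts scaling with unique patients, and on Phase 1 data from 2014–2016.

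This is a secondary, observational analysis. Retention does not use the one-year visit offset, and neither the primary nor the main secondary objective is touched.

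**What to change.** State one window per measure and use it for both count and offset, in Table 9 and in 11.3.1 alike. The simplest choice keeps the Table 9 counts and changes the offset to patients seen over 2 years for initiation and over 3 years for recognition. At the system with a shorter pre-randomization period, the available period should serve for both. The alternative is to redefine count and offset together as one-year measures in both sections, which is equally sound but uses fewer events.

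The cost is a line or two in the Protocol or the separate observational analysis plan. Protocol Section 9.3.5 already has the 3 years of pre-randomization data drawn for randomized and non-randomized clinics, so no new extraction should be needed. If the separate plan already fixes matched windows, a cross-reference from 11.3.1 is enough.

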11.3.2 Secondary Modelling of Primary Outcome

Secondary analyses of the primary outcome measure with adjustment for additional covariates that are potential confounders will be provided in the standalone Statistical Analysis Plan (SAP). The exact approach to identifying which covariates will be included will be described in the SAP, including the process for selecting the appropriate analytic method.

11.3.3 PROUD Intervention vs. Other “Exemplar” Models of OUD Care

We will compare outcomes in ten exemplar clinics in 4 health systems to outcomes in the PROUD intervention clinics. We will compare implementation outcomes and patient outcomes (identical outcomes as for primary and secondary objectives) in the 2 years after randomization in those clinics, to the PROUD intervention clinics. Analyses for this secondary observational objective will follow the same general modeling approach as described above for the primary and secondary main outcomes (e.g., implementation and patient outcomes). To account for possible differences between the exemplar clinics that were not included in the trial as compared to the PROUD intervention clinics included in the trial, we will adjust for any covariate found to differ between these two sets of clinics (PROUD Intervention vs Exemplar) in the 3 years prior to randomization in the regression models.

11.3.4 Differences in Impact of PROUD on the Primary Outcome across Age, Sex and Race/Ethnicity

Given the NIH requirement to perform subgroup analyses of the primary outcome on the basis of sex, race and ethnicity, and the importance of understanding how the MA Model performs in individuals < 26 years, we plan to conduct analyses of subgroups based on: age (< 26 vs older); sex; race and ethnicity (categories depend on final race/ethnicity data available). An interaction term between demographic subgroup and treatment assignment can be used to evaluate whether the demographic factor moderates the treatment effect. Any such comparisons will likely be underpowered and must be interpreted with caution. Our hypothesis is that the PROUD intervention will result in differences in the main outcomes across sex, age, race and ethnicity,⁷³ so that we hypothesize that coefficients for interaction terms will not be equal to zero.

11.3.5 Evaluate Secondary Outcomes

Secondary outcome measures outlined in Section 8.3.2 are analyzed using methods similar to those used for the primary and secondary outcomes.

11.4 Rationale for Sample Size and Statistical Power

Given that Phase 1 of CTN-0074 found that only six health care systems (HCS) were eligible for Phase 2, the power calculations focus on 6 HCS, with each HCS contributing two clinics. One clinic from each health care system will be randomized to implement the PROUD intervention, while the other will continue with usual primary care (UPC). Simulations were conducted to calculate the power associated with various values of the treatment effect, which is parameterized as the mean of the primary outcome measure in the intervention clinics divided by the mean in the UPC clinics. Of ultimate interest in the calculations presented here is whether, with the sites selected in Phase 1, there will be sufficient power (>80%) to detect at least a 5-fold increase in the number of patient days of OUD treatment (per 10,000 participants) associated with implementation of the PROUD intervention as compared to UPC. To accomplish this, we considered various values of the treatment effect and calculated the corresponding statistical power via simulation.

11.4.1 Power Simulations – Primary Objective

11.4.1.1 Data-generation and Analysis Model

In our power simulation, there were 6 HCS and 2 clinics within each HCS (one clinic assigned to the intervention and one to UPC), making 12 clinics in all. The outcome variable for each clinic is *Treated Days per Patient Seen*, which with actual data, we would calculate by dividing the total number of treated days at the clinic during 2 years of follow-up by the total number of unique patients seen by the clinic during that same time period. In addition, we would use Phase 1 data to calculate an approximation of the magnitude of the association between the number of OUD-treated days per patient seen pre- and post-randomization. The analytic model previously specified would require four years of data for this estimation, however only three years of data are available from Phase 1. Thus, data was generated in a recursive fashion as follows:

Step 1: Estimate via regression the relationship between the number of OUD-treated days per patient seen in the last two years of Phase 1 data and the same measure for the first two years of the Phase 1 data. This corresponds to regression of the outcome for FYs 2015-2016 on FYs 2014-2015 (see Section 11.4.1.2). Since the Phase 1 data does not capture four years of data we cannot directly model the relationship between non-overlapping years. For this model, a random effect capturing the correlation of clinics from the same health care system was not included (see Section 11.4.1.2).

Step 2: Using this estimated regression model, predict the outcome measure for the next two- year period (FYs 2016-2017), and repeat to generate the outcome measure for the post-randomization period which roughly will correspond to FYs 2018-2019.

Step 3: For half of the clinics, when generating the data for the post-randomization period a covariate for treatment assignment is also included.

The details of this simulation approach will be included in the first version of the standalone SAP.

11.4.1.2 Parameters Used to Generate the Simulated Data

Table 12 provides the number of OUD-treated days during a two-year period per patient seen in the clinic. These values were used to estimate the parameters for Steps 1 and 2 in the algorithm summarized in Section 11.4.1.1.

Table 12. Number of Days Treated for OUDs (with buprenorphine or injectable naltrexone) per Patient Seen at 2 Phase 1 Clinics in Each of 6 Health Care Systems (HCS)

HCS	Fiscal Years 2014-2015		Fiscal Years 2015-2016	
	Clinic 1	Clinic 2	Clinic 1	Clinic 2
1	0.031	0.008	0.085	0.019
2	0.339	0.215	0.354	0.173
3	0.001	0.022	0.001	0.076
4	0.015	0.089	0.021	0.431
5	0.007	0.002	0.004	0.002
6	1.385	0.715	1.361	0.703

From Table 12 we fit a random effects model with a fixed intercept for the number of OUD-treated days per patient seen in FYs 2015-2016 as a function FYs 2014-2015 where the random effect captures the correlation between clinics arising from the same health care system. The estimated intercept was 0.05, the coefficient for FYs 2014-2015 was 0.94 and the variance of the random effect was not significantly different from zero. Thus, the predictive model used to generate the simulated data did not include a random effect for health care system (see Section 11.4.1.1).

11.4.1.3 Results of Simulations

It was also of interest to assess the potential increase in power associated with inclusion of the baseline value of the primary outcome measure in the regression model. Table 13 presents power results for the 0.05-level one-tailed test, based on 10,000 iterations per table cell for two models: one without adjustment for baseline, and one with baseline included as a covariate.

Table 13. Power Results for a 0.05-level One-Tailed Test, Based on 10,000 Iterations Per Cell

k-fold Increase in Primary Outcome (Treatment Effect)	Model	
	No Adjustment for Baseline	Inclusion of Baseline as a Covariate
1.00	5%	5%
1.03	8%	14%
1.06	13%	28%
1.09	18%	46%
1.12	24%	65%
1.18	39%	92%
1.24	54%	99%

Based on Table 13, there is at least 80% power to detect an 18% increase in the number of OUD-treated days per patient seen. Thus, with two clinics in each of six health care systems, the study is sufficiently powered to detect the targeted 5-fold increase in the primary outcome measure. As anticipated, there is a substantial gain in power when the baseline value is included as a covariate in the primary outcome model.

11.4.2 Power Simulations – Secondary Objective

We investigated the power of the primary Objective 2 analysis via simulation. Among individuals in the intervention clinic with an EHR documented OUD diagnosis pre-randomization, not all will visit the PROUD NCM and receive treatment with buprenorphine or injectable naltrexone (hereafter “treated for OUDs”). We explored how the power is affected by the proportion of patients with a prior OUD diagnosis who are treated for OUDs (p_{trt}). Based on the table below, and our expectation that the PROUD clinics will treat over 15% of patients with OUDs, we expect to have adequate power for our secondary objective.

We assumed the following sample sizes for the number of patients with a prior OUD diagnosis over a 3-year period from the Phase 1 data, reflecting the 3-year baseline period of PROUD during which patients with an OUD diagnosis will be identified:

site_id	clin_num	clin	nOUD
A	1	A1	9
A	2	A2	12
C	1	C1	63
C	2	C2	39
E	1	E1	58
E	2	E2	200
I	1	I1	100
I	2	I2	49
J	2	J2	10
K	1	K1	388
K	2	K2	290

[figure not shown]
We generated individual-level outcome data within each of the 12 clinics as follows. First, we randomly assigned one of the two clinics within a HCS to receive the PROUD intervention. Then, for each patient from a PROUD intervention clinic with a prior OUD diagnosis, we identified whether that patient was treated for OUDs by the nurse (with probability p_{trt}). Of the patients treated for OUDs by the nurse, we assumed that the probability that they are persistently treated is 50%. Among patients who are able to be treated for OUDs and are persistently treated, we generated outcome data from a Poisson distribution with mean number of acute care days over a two-year period (time-frame of PROUD outcome ascertainment) equal to that of individuals without a prior OUD diagnosis based on Phase 1 data ($=1.7$ days). Among the remaining patients (including those who are not treated for OUDs or who are not persistently treated), we generated outcome data from a Poisson distribution with the corresponding mean number of acute care days equal to that among individuals with a prior OUD diagnosis based on the Phase 1 data ($=8.2$).

days). To each simulated dataset, we fit the Poisson mixed-effect model described in the analysis section.

Note that these initial power calculations were not based on simulating clinic-level random effects. In another set of simulations that did generate clinic-level random effects, the type I error rates were no longer accurate. This is because under the small number of clinics per treatment arm (intervention vs. usual care), generating outcome data in this way yielded imbalance in the mean number of acute care days in the intervention versus usual care arm. Imbalance in the rates of acute care across treatment arms is a concern; as described in our analysis plan above, we plan to adjust for baseline utilization along with other covariates that could account for differential utilization across clinics.

Results

The following plot and table show the power across different values for the proportion of patients within PROUD clinics who are treated for OUDs (p_{trt}). We see that power was >0.90 in scenarios where more than 20% of patients with recognized OUDs are treated for OUDs ($p_{\text{trt}} > 0.20$).

p_trt	Power	Type 1 error
0.10	0.468	0.056
0.15	0.798	0.046
0.20	0.926	0.046
0.25	0.988	0.030
0.30	0.992	0.064
0.35	0.996	0.020
0.40	0.998	0.036

